4.3 Tissue and Data Processing and Storage

4.3.a: Phase 1: First 100 Biopsies: All samples will be placed in sterile, iced saline on the catheterization laboratory table. Immediately after the last biopsy is obtained, the research biopsies will be given to the MM-HFpEF study staff who will place samples on a sterile dry towel to remove saline. One sample will be placed in formalin and will be subsequently embedded in paraffin (FFPE) at the MM-HFpEF Core Laboratory. The other two samples will be flash frozen in individual containers of liquid nitrogen.

4.3.b: Phase 2: Second 200 Biopsies: Samples will be processed as decided by the MM-HFpEF Core Laboratory and the HFpEF Tissue Working Group as Phase 1 enrollment nears completion.

For both phases, venous blood samples (5 ml) will be taken from the superior vena cava, placed in centrifuge tubes (red top), processed in the bio-accession and processing laboratory (BAP) with serum aliquoted into 0.5 ml samples, frozen and shipped with the biopsy specimens to the MM-HFpEF Core laboratory. The samples will be shipped to the MM-HFpEF Core Laboratory where the formalin fixed samples will be embedded in paraffin and frozen samples will be stored at -80 degrees. Deidentified (MM-HFpEF Study #) corresponding baseline, procedural and post-procedural clinical data will be provided within 90 days to the Heart Share Data Translation Center. Follow up data (HF hospitalization, death, presumed cause of death) will be provided yearly for five years after the biopsy.

The data for this trial will be collected in trial-specific electronic data collection forms from source documents by the research staff during the study visit. The study coordinators will be responsible for transmitting the participant unique non-PHI identifiers using standardized data collection instruments to the Heart Share Data Translation Center at Northwestern University. The research coordinators and investigators will perform manual data entry from source documents.

4.4 Risks associated with Study Procedures

Right Heart Catheterization (RHC)

Most RHC performed in this study will be clinically indicated. Few studies have reported the risk of RHC.⁷⁴ The RV EMB procedure includes sheath placement in the jugular vein which is part of the RHC procedure as well. No studies have reported the risk of only passing a pulmonary artery catheter through the right heart and pulmonary artery for hemodynamic measurements. Thus, complications cited for RHC are not necessarily additive to RV EMB. Complications in patients undergoing RHC (n=5556) from 2002 to 2013 for any indication at Mayo Clinic in Rochester, MN were recently reported.⁷⁴ Overall, complication rates were low (0.216% for RHC) with no deaths attributed to the procedure. For RHC alone, there were no pneumothoraces, 0.036% with ventricular tachycardia, no hemoptysis, 1.3% with worsening tricuspid regurgitation, and no cardiac tamponade events.

Right Ventricular (RV) Endomyocardial Biopsy (EMB)

A recent joint position paper on EMB from the European, Japanese and American HF Societies⁷¹ concluded that EMB is associated with a low rates of major and minor (Table).⁷¹ Some studies reported complications separately for RV and LV EMB while others did not categorize by biopsy site. Patient characteristics including clinical stability and underlying cardiac problem, EMB site (right vs left ventricle), procedural volume and operator expertise were the most important determinants of EMB risk. For example, risk is higher in patients hospitalized with cardiogenic shock due to fulminant myocarditis vs in stable outpatients with NYHA class 2 HFpEF symptoms undergoing EMB to rule out infiltrative vs hypertensive heart disease. It can be difficult to determine whether observed complications are due to the underlying disease process or the EMB itself (i.e. higher rates of reported arrhythmia in a series confined to patients undergoing biopsy for myocarditis (table)). One paper had higher rates of complications than other studies (table, red text). Other papers reported that EMB performed in heart transplant patients had lower complication rates than in native hearts.⁷⁵ As transplant patients do not have a fully intact parietal pericardium, they should have lower rates of tamponade. The discharge diagnosis of the hospitalizations where the EMB was performed in non-transplant patients included HF (58%), cardiogenic shock (19%) and myocarditis (4%). The report included non-teaching hospitals where rates were 6x higher and accounted for 25% of the complications (with only 6% of the procedures). In teaching hospitals, the rates were 0.5% vs 0.2% in non-tx vs tx. The rate of complications at the MM-HFpEF Core Laboratory in 3,459 patients was 0.17% for sustained arrhythmia events (requiring pharmacological or electric cardioversion) and 0.06% for pericardial effusion that required pericardiocentesis.

Management of cardiac perforation during EMB includes immediate pericardiocentesis and autotransfusion from the pericardium, close monitoring, and consultation with a cardiac surgical service. Urgent surgical repair of the perforation site may be required in patients with ongoing bleeding or instability related to the perforation.

For RV EMB, few studies have systematically evaluated damage to the tricuspid valve with worsening tricuspid regurgitation as most institutions have not routinely used echocardiographic guidance for EMB or performed routine assessment of tricuspid regurgitation before and after EMB.⁷⁴ Since the publication of the HF society position paper, complications in patients undergoing EMB (n=3846) for any indication at Mayo Clinic in Rochester, MN (2002 to 2013) were reported.⁷⁴ Overall, complication rates were low (0.208% for EMB) with no deaths attributed to the procedure and individual complication rates similar to those quoted in the position paper (Table). Echo was used in a minority of EMB and this may result in over (indication bias in complex cases) or under (no systematic assessment) estimation of rates of worsening tricuspid regurgitation. In the Mayo study, worsening TR occurred in 5.1% of EMB cases (most asymptomatic and most in cardiac transplantation patients who have many repeated EMB).

Importantly, in large (> 3000 patients) contemporary series from two of the teaching hospitals who will be involved in this study, the risk of death associated with EMB was 0% and the risk of serious complications (tamponade or ventricular arrhythmias) was each less than 2 per 1000 procedures.^{74,76}

Major Complications (cited for RV or LV EMB) ⁷¹	Reported Risk range ⁷¹	Risk reported in each study with at least 500 RV (if reported separately) EMB (Table S1 in ⁷¹)
Death	0% to 0.07%	One study 0.07% - all others 0%
Cardiac hemopericardium or tamponade	0% to 6.9%	6.9%, 0.05%, 0.16%, 1.5%, 0.8%, 0.45%, 0.81%, 0.1%, 0.4%, 0.3%
Pneumothorax/air embolism	0% to 0.8%	0.8%, 0%, 0.07%, 0%
Thromboembolism	0% to 0.32%	0%, 0%, 0%, 0%
Valvular trauma (Tricuspid Regurgitation)	0.02% to 1.1%	1.1%, 0.02%, 0.6%
Severe arrhythmia or atrioventricular block	0% to 11%	11%, 0.13%, 17.5% (all myocarditis pts), 0.8%, 0.19%, 0.61%, 0%
Minor Complications		
Transient chest pain	0% to 1.8%	1.8%, 0.1%, 0.19%, 0.61%, 0%,
Deep Vein Thrombosis	0.23% to 3.8%	3.8%, 0.23%,
Vascular access site hematoma/nerve palsy	0% to 0.64%	0.4%, 0%, 0.1%, 0.19%, 0%, 0.64%
Hypotension/vaso-vagal syncope	0% to 4.3%	0.06%, 0.78%, 4.3%
Arterial trauma/vascular damage	0.32% to 2.8%	NA for RV EMB
		Single study with higher rates for all complications

4.5 Strategies to mitigate Risk to Participants

To minimize risk, operators will need to have averaged at least 20 to 50 RV EMB per year⁷¹ for at least the preceding four years (exclusive of COVID impact in 2020). Continuous electrocardiographic and pulse oximetry monitoring and intermittent blood pressure (if no arterial line used) will be monitored. Echocardiographic assessment for tricuspid valve structure and regurgitation and for pericardial effusion is assessed during each biopsy and at the end of the procedure. After the research EMB, patients are observed for clinical stability in the catheterization laboratory post procedural area as per local clinical protocols and as deemed necessary by the EMB operator. Repeat echo imaging of tricuspid valve structure and regurgitation and for pericardial effusion is performed immediately after the procedure in the catheterization laboratory. Only RV EMB will be performed (lower risk of stroke and arterial bleeding). Only clinically stable patients without high-risk features (see **3.2.b: Exclusion criteria**) will be included.

4.5 Tissue Analysis

4.5.a. Background: The MM-HFpEF study seeks to use discovery multi-omics to determine if there are novel, therapeutically relevant and varied (myocardial pathophysiologic heterogeneity) mechanisms mediating myocardial dysfunction in HFpEF. Most studies of human HFpEF tissue have been hypothesis driven analyses of candidate pathways. Unbiased assessment of differences in gene expression (transcriptomics) and/or protein abundance (proteomics) coupled with bioinformatic analyses to determine the pathways indicated by gene or protein changes (“omics” analysis) or integrated gene and protein changes (multi-omics) can be used to discover novel transcriptional or translational changes mediating myocardial pathology in HFpEF.

Transcriptional changes may mediate cardiac pathology in cardiomyopathies⁷⁷ and HFpEF.^{19,49} However, in endstage cardiomyopathies, dramatic differences in phenotype were unaccompanied by differences in gene expression.⁷⁸ Further, transcriptional changes did not correlate tightly with phenotype or protein changes before and after myocardial recovery in HFrEF⁷⁹ or in hypertrophic cardiomyopathy (HCM) versus controls.⁸⁰ Recent work suggests that several myocardial pathophysiologic changes maybe be predominately or jointly controlled at the translational level^{81,82} and thus, study of the proteome may reveal novel or complementary pathophysiologic information beyond changes in gene expression.

Two studies performed transcriptomics on myocardial tissue (bulkRNAseq) using LV or RV samples from HFpEF as compared to HFrEF and/or NF Controls. Both identified 13,000 to 14,000 genes but in one study (LV surgical samples from patients undergoing surgical revascularization for coronary disease with or without evidence of HFpEF), only 743 (5%) genes were differentially expressed (DE) in HFpEF versus NF controls.¹⁹ Most (719) DE genes were down regulated. In the other study with a larger sample size, 67% of genes were DE in HFpEF (RV EMB in patients with rigorously documented HFpEF) versus NF controls and 52% of genes were DE in HFrEF vs NF Controls.⁴⁹ Up-regulated (but not down-regulated) genes in HFpEF were no longer significant after adjustment for HFpEF risk factors. Both the HFpEF transcriptomic studies used bioinformatic pathway analyses to interpret the DE gene data and demonstrate alterations consistent with various theories for the pathogenesis of HFpEF.

Gene expression changes in single cells (scRNAseq) or in nuclei isolated from tissue (snRNAseq) may provide greater pathophysiologic insight. For both technical and biologic reasons, fewer genes are usually detected with sc- or snRNAseq (characterized as detecting 10-40% of the transcriptome⁸³). To date, scRNAseq or snRNAseq studies in HFrEF and/or NF Controls^{77,84-86} or in endstage cardiomyopathies⁷⁸ have been performed. The small size of EMBs make snRNAseq analyses challenging but the MM-HFpEF Core Laboratory has used novel methods to perform snRNAseq in preliminary studies in HFpEF EMB.

Proteomics studies in HF and cardiomyopathies have been more limited. In cryopreserved LV tissue from autopsy subjects with or without diastolic dysfunction, mass spectrometry (MS) with isobaric tags to characterize the myocardial proteome revealed 1976 proteins with 57 DE proteins.⁸⁷ Network analysis indicated endoplasmic reticulum (ER) stress was significantly altered in the diastolic dysfunction group with down regulation of key proteins involved in the unfolded protein response as reported by others in experimental HFpEF.⁸ Another study of LV tissue from diverse HFpEF and NF Control cohorts used newer proteomic techniques but identified only 1043 proteins of which 12 were DE.²⁶ A comprehensive MS study of the normal human cardiac proteome⁸⁸

identified approximately 8000 proteins were identified in the LV and RV. The MM-HFpEF Core Laboratory has evaluated several proteomic approaches in extensive preliminary studies in HFpEF.

A limited number of studies have examined alterations in metabolism in HFpEF, with the majority examining a single aspect of metabolism such as mitochondrial and oxidative phosphorylation integrity,^{18,36} nicotinamide adenine dinucleotide (NAD⁺) integrity^{59,89}, somatotropic axis homeostasis,²⁰ osteopontin mediated disruption of 2-Oxoglutarate Dehydrogenase-Like (OGDHL) mitochondrial signaling.⁶³ The MM-HFpEF Core Laboratory performed targeted metabolomics and select transcriptomics in RV myocardium from HFpEF, NF Controls and HFrEF showed evidence of decreased fatty acid oxidation in HFpEF relative to NF Controls but no evidence of compensatory increases in ketone utilization, glycolysis or branched chain amino acid metabolism, suggesting insufficient regeneration of citric acid cycle (TCA) intermediates (reduced anaplerosis) and fuel inflexibility. Despite much higher rates of obesity in HFpEF, FA oxidation appeared lower in HFpEF than HFrEF. Tissue metabolomic findings did not correlate with plasma metabolomic findings and methylhistidine, a post-translationally modified amino acid was increased in myocardium and plasma, suggesting stress induced myofibrillar turnover.⁵⁰

4.5.b. Approach: As outlined above, the MM-HFpEF Core Laboratory has performed bulk RNAseq transcriptomics and metabolomic studies in HFpEF with findings implicating unique pathways in HFpEF or HFpEF subtypes.^{49,50} The Core laboratory has also performed preliminary (data unpublished) snRNAseq studies and proteomics studies in HFpEF. The larger MM – HFpEF study seeks to build on these preliminary findings and to confirm and extend these “first in HFpEF” discovery omics studies.

The Phase 1 approach in the first 100 patients will be to collect extensive clinical data and perform digital histology and spatial transcriptomics (FFPE samples) with spatial proteomics in a subset. In frozen samples, bulkRNAseq (one frozen biopsy specimen) and (unlabeled) LC-MS MS proteomics (data independent analysis, other frozen biopsy specimen) will be performed in the first 100 patients. This multiomics (histology, transcriptomics, proteomics) analysis will allow unique insight into transcriptional and translational regulation of myocardial structure and function.

In the second 200 HFpEF subjects undergoing research EMB (Phase 2), sample processing techniques, appropriate controls and biologic analyses will be designed by the MM-HFpEF Core Laboratory and the Heart Share MM-HFpEF Working Group to build on findings in Phase 1, evolution in omics technology and other advances in knowledge. Phase 2 analyses will include but not be limited to, snRNA-seq, targeted metabolomics, myofilament functional assessments, further spatial transcriptomic or proteomic analyses, further HFpEF phenogroup characterization and more in-depth study of specific pathways suggested to mediate HFpEF pathophysiology based on Phase I findings.

5.0 INFORMED CONSENT AND STUDY MONITORING

The MM-HFpEF study will report to the Heart Share Observational Study Monitoring Board (OSMB). The Heart Share OSMB was established by the NHLBI in accordance with NIH policies and is responsible for monitoring of patient safety and review of study performance. The OSMB consists of a chair, clinicians or scientists with expertise in heart failure, bioethics, and biostatistics. An NHLBI scientist other than the NHLBI’s Project Scientist serves as the Executive Secretary to the OSMB. The OSMB meets at regular intervals (at least twice per year) and at other times as necessary, as described in the HeartShare OSMB charter. The purpose of monitoring is to (1) verify that the rights and well-being of human participants are protected; (2) ensure that the reported study data are accurate, complete, and verifiable from source documents; and (3) ensure that the conduct of the study is in compliance with the currently approved protocol/amendment, with Good Clinical Practices, and with applicable regulatory requirements.

Informed Consent

The site investigator, or a person designated by the site investigator, will fully inform the participant of all pertinent aspects of the study including the review of the IRB-approved informed consent form. All study procedures and

potential risks will be discussed in detail with each participant. The Informed Consent Form (Consent) will be signed and personally dated by the participant prior to the commencement of any study procedures. All participants will receive a copy of the informed consent form. Electronic copies of the signed Consent forms will be retained at each study site.

Adverse Events

All adverse events occurring within the MM-HFpEF study will be recorded and reported, starting at the beginning of the RHC/EMB procedure and continuing for a 30 day period after the RHC/EMB has been completed.

Adverse events are defined as:

- **Adverse event:** An adverse event (AE) shall be considered any detrimental change in the patient's condition.
- **Anticipated adverse event:** Anticipated adverse events are defined for each of the protocol procedures in the sections specifically written for those procedures.
- **Unanticipated adverse event:** Any adverse event that results in risk or harm to the participant or others that differs from the known, predicted possible effects of the research protocol. An unanticipated adverse event is one that varies in nature, intensity, or frequency from information in the informed consent document.
- **Serious adverse event:** Any event that results in death, inpatient hospitalization or prolongation of existing hospitalization, a persistent or significant disability or incapacity. Important medical events that may not result in death, be life-threatening, or require hospitalization may be considered a serious adverse event when, based upon appropriate medical judgment, they may jeopardize the patient or participant and may require medical or surgical intervention to prevent one of the outcomes listed above.

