After the research EMB and post-EMB imaging, other clinically indicated procedures (i.e. exercise hemodynamics, drug studies for pulmonary vascular function) to further evaluate HFpEF will be performed. Patients may participate in other research protocols as long as the studies do not interfere with the study entry algorithm (figure) and the ability to perform the EMB.

After the research EMB and any other clinically indicated procedures, patients will be observed for clinical stability in the catheterization laboratory post procedural area and then discharged according to routine post-procedural practice at the participating site. At discharge and at 30 days post procedure, the clinical record will be reviewed, and a case report form completed documenting any procedural related adverse events due to research RHC or EMB.

Up to 300 patients will be enrolled over a five-year period at up to 10 sites participating in the MM-HFpEF study.

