3.2 Study Population

3.2.a: Inclusion criteria: Patients with known or suspected HFpEF will be identified by electronic medical record searches, referrals from clinicians, focused screening in the clinical practice including patients scheduled for RHC to diagnose or assess severity of HFpEF, responses to posting of research opportunities or review of patient lists from previous HFpEF studies.

HFpEF criteria

1. Age ≥ 30 years.
2. Left ventricular ejection fraction $\geq 50\%$ measured by echocardiography, CMR or MUGA (measured within one year + clinical stability)
3. Definition of HFpEF: signs and/or symptoms of HF, NYHA functional class II-IV, and at least one of the following:
 - a. Elevated BNP (≥ 75 pg/ml in sinus rhythm or ≥ 225 pg/ml in atrial fibrillation/flutter) or NTproBNP (≥ 225 pg/ml in sinus rhythm or ≥ 675 in atrial fibrillation/flutter) at baseline. Choice of BNP or NTproBNP is based on availability at each clinical center.
 - b. Prior HF hospitalization (primary reason for the hospitalization is HF with elevated natriuretic peptide levels [using the thresholds listed above], requiring IV diuresis for HF, or pulmonary edema or pulmonary vascular congestion on chest radiography).
 - c. Previously documented elevated pulmonary capillary wedge pressure (PCWP) at rest (≥ 15 mmHg) or during exercise (≥ 25 mmHg for supine exercise or PCWP/cardiac output ratio ≥ 2 mmHg/L/min for upright exercise).
 - d. Elevated H₂FPEF score⁶⁹ (≥ 5) or HFA-PEFF⁷⁰ score (≥ 5).

Suspected HFpEF criteria

1. Age ≥ 30 years.
2. Left ventricular ejection fraction $\geq 50\%$ measured by echocardiography, CMR or MUGA (measured within one year + clinical stability)
3. Signs and/or symptoms of HF, NYHA functional class II-IV and all of the following:
 - a. Does not meet BNP or NT-proBNP criteria for HFpEF (above)
 - b. No prior HF hospitalization meeting HF criteria (above)
 - c. No previous hemodynamic catheterization documentation of HF (as above)

3.2.b: Exclusion criteria:

According to current guidelines,⁷¹ patients deemed at increased risk of right ventricular (RV) septal EMB complications as evidenced by any of the below will be excluded.

1. Inadequate echo or fluoroscopic images.
2. Neck anatomy unfavorable for jugular venous cannulation
3. Therapy with direct oral anticoagulants without cessation for a period (age, renal function, and agent specific) deemed adequate to normalize coagulation according to local clinical guidelines.

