4. Previous or ongoing therapy with warfarin with INR ≥ 1.6 measured day before or of EMB
5. Platelet count $< 50,000/\text{ml}$
6. Active bleeding or coagulation disorder
7. Infection or fever
8. Endocarditis
9. Pregnancy
10. Intracardiac thrombus
11. RV Aneurysm
12. Clinically significant tricuspid, pulmonary or aortic valve stenosis
13. Tricuspid or pulmonary mechanical valve prosthesis
14. Left bundle branch block

A known contrast media hypersensitivity is not a contraindication as contrast is not routinely used but the presence of contrast media hypersensitivity should be noted to preclude use. For patients with an indication for anticoagulation (ie atrial fibrillation), who are treated with warfarin, bridging according to local protocols if deemed advisable by the patient's clinician.

Patients with hemodynamically significant left valve disease, pericardial disease, known hypertrophic cardiomyopathy, severe non-revascularized coronary disease, or known inflammatory (i.e. myocarditis or sarcoidosis) or infiltrative (i.e. amyloidosis) cardiac diseases or known non-group 2 pulmonary hypertension are excluded.

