3.4 Primary Study Data Collected from Review of Clinical Records and Study Procedures

3.4.a: Medical History and Physical Examination: age, sex, history of hypertension, diabetes, hyperlipidemia, coronary disease, atrial fibrillation, pacemaker, myocardial infarction, chronic kidney disease, obesity (BMI ≥ 30), collagen vascular disease, lung disease (obstructive, restrictive), previous thoracic radiation or valve disease and blood pressure, heart rate, height, weight.

3.4.b: Laboratory values: creatinine, blood urea nitrogen, NT-proBNP, Hgb, Hct, platelets, white blood cells, and INR day of or day before procedure (only if on warfarin and holding for EMB).

3.4.c: Electrocardiogram: rate, rhythm (sinus, atrial flutter or AF, ventricular pacing), QRS duration, LBBB pattern (yes/no)

3.4.d: Echocardiogram: Left atrial dimension and/or volume (method), LV end diastolic dimension and/or volume (method), LV septal and posterior wall thickness, LV ejection fraction (value/method), right ventricular size (semiquantitative) and function (semiquantitative), aortic, mitral, tricuspid and pulmonary valve function (stenosis or regurgitation grade)

3.4.e: Resting hemodynamics: HR, systemic blood pressure, RA (a,v,mean), RV (systolic, end-diastolic), PA (systolic, diastolic, mean), PCWP (a,v, mean), cardiac output method (Fick indirect, Fick direct, thermodilution), cardiac output, cardiac index, PVR, PA compliance.

3.4.f: Passive Leg Raise hemodynamics: PCWP (a,v, mean)

3.4.g: Clinically indicated exercise hemodynamics (if performed): Exercise method (arm, bike upright, bike supine, other), peak level (watts, other), and same hemodynamic measures as in 3.4.e (as available).

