3.5 Primary Safety Data Collected

3.5.a: Pre-EMB echo: Echocardiographic tricuspid regurgitation grade (semi-quantitative) and pericardial effusion (window, dimension)

3.5.b: Immediate post-EMB echo: Echocardiographic tricuspid regurgitation grade (semi-quantitative) and pericardial effusion (window, dimension), tamponade physiology (yes/no)

3.5.c: Research RHC complications: death, chest pain, hemoptysis, pneumothorax, access site bleeding or hematoma exceeding usual expected severity, new atrial fibrillation/flutter, other clinically significant arrhythmias (ventricular tachycardia requiring therapy, heart block requiring therapy), pulmonary artery perforation, new or worsening tricuspid regurgitation.

3.5.d: Research EMB complications: death, chest pain, hemoptysis, pneumothorax, access site bleeding or hematoma exceeding usual expected severity, new atrial fibrillation/flutter, other clinically significant arrhythmias (ventricular tachycardia requiring therapy, heart block requiring therapy), new or worsening tricuspid regurgitation, new pericardial effusion requiring admission or serial echocardiography without intervention, tamponade requiring percutaneous pericardiocentesis, tamponade requiring surgical pericardiocentesis with or without myocardial repair.

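### Adverse event recording opens at the catheterization, so an event during an anticoagulation hold made beforehand for the research biopsy goes unrecorded

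*Protocol*

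**What the plan says.** **Adverse event window.** Section 5.0 (Informed Consent and Study Monitoring, Adverse Events) has all adverse events recorded and reported, "starting at the beginning of the RHC/EMB procedure and continuing for a 30 day period after the RHC/EMB has been completed". It defines an adverse event broadly, as any worsening of the patient's condition.

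**Anticoagulation conditions for entry.** Section 3.2.b presents its numbered exclusions as markers of raised risk from right ventricular septal biopsy. Item 3 excludes "Therapy with direct oral anticoagulants without cessation for a period (age, renal function, and agent specific) deemed adequate to normalize coagulation". Item 4 excludes "Previous or ongoing therapy with warfarin with INR ≥ 1.6 measured day before or of EMB". For warfarin patients with an indication such as atrial fibrillation, the text below the list allows "bridging according to local protocols if deemed advisable" by the patient's clinician. Section 3.4.b ties the warfarin interruption to the biopsy: the INR is collected "only if on warfarin and holding for EMB".

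**Other safety data.** Section 3.1 has the clinical record reviewed at discharge and at 30 days, with "a case report form completed documenting any procedural related adverse events due to research RHC or EMB". Section 3.5.d begins "Research EMB complications: death, chest pain, hemoptysis, pneumothorax, access site bleeding or hematoma exceeding usual expected severity" and continues with arrhythmia, tricuspid and pericardial events. Neither it nor 3.5.c has an item for stroke, embolism or venous thrombosis. The table in 4.4 names thromboembolism as a major complication and "Deep Vein Thrombosis" as a minor one.

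**The concern.** The entry rule creates a period of reduced anticoagulation before the procedure, and the safety record starts only when that period ends. A stroke, a systemic embolism or a bleed on bridging therapy in that period is a harm that taking part can cause, yet following the protocol as written would not record it. The worst case is the least visible: a participant whose event keeps them from reaching the catheterization laboratory never enters the window.

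The protocol states that participants have no direct benefit and rests its risk/benefit judgement on low risk (5.0 Ethical Considerations). It also charges the Observational Study Monitoring Board with participant safety and complete data. The board cannot weigh events that are not collected. The omics aims are not affected; the issue is the completeness of the safety record.

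**Working it through.** The protocol gives no figure to reproduce. The check sets its time rules side by side and asks, for each interval, which data source would catch a thromboembolic event.

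| Interval | What the protocol requires | Would the event be recorded? |
|---|---|---|
| First anticoagulation change to start of RHC/EMB | Direct oral anticoagulant stopped (3.2.b item 3) or INR below 1.6 (item 4), bridging optional | No |
| Start of RHC/EMB to day 30 | All adverse events (5.0) | Yes under 5.0; not clearly under 3.1 or 3.5 |
| After day 30 | Yearly heart failure hospitalization, death and presumed cause of death (4.3) | Only if fatal |

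**Is the first interval covered elsewhere?**
- 3.5.a and 3.5.b are echocardiograms just before and just after the biopsy.
- 3.5.c and 3.5.d list complications of the research catheterization and biopsy.
- The 3.1 form is limited to events due to those procedures.
- The follow-up data in 4.3 are counted from the biopsy. The annual chart review in 3.3 is counted from enrolment, but its purpose is to relate tissue findings to outcomes, and the items in 4.3 do not include non-fatal stroke or embolism.

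No source covers the interval.

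**Can the interval fall after consent?** Section 5.0 requires consent before any study procedure but does not place it relative to the hold. It can therefore fall after consent; how often is unknown.

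**Are the post-procedure rules consistent?** Section 5.0 asks for all adverse events to day 30, while the 3.1 form asks only for those due to the research procedures. Section 5.0 also says anticipated events are defined in the procedure sections. The 4.4 table names thromboembolism and deep vein thrombosis, and 3.5.c and 3.5.d list neither. These are differences between sections, not a gap in the 5.0 window.

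**Size.** The protocol gives neither the number of anticoagulated participants, nor the length of the hold, nor an event rate. As an illustration only, assume that 30% to 60% of the maximum 300 participants are anticoagulated and that thromboembolism occurs in 0.1% to 1% of interruptions:
- 300 × 0.30 = 90 and 300 × 0.60 = 180 participants;
- 90 × 0.001 = 0.09 and 180 × 0.01 = 1.8 events.

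All four inputs to this range are assumptions. A rate per interruption also includes the time after the procedure, which 5.0 does record, and the calculation counts holds made for clinical reasons or before consent. On these assumptions the unrecorded share is below 0.09 to 1.8 events. Bleeding on bridging is not included.

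**The case against.** **Post-procedure events are already covered.** The hold continues after the biopsy until anticoagulation is effective again, and that part lies inside the window. The complication lists in 3.5 do not restrict the duty in 5.0 to record all adverse events. This stands. A reader might infer that every embolic event while anticoagulation is held is lost, or that the reported rates of thromboembolism and deep vein thrombosis would be biased low. The documents do not support that for events from the procedure to day 30. What remains there is that a site completing the 3.1 form and the 3.5 lists is not prompted for events that 5.0 wants.

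**The 4.4 table does not measure the gap.** Applying its deep vein thrombosis range to 300 participants gives 300 × 0.0023 = 0.69 to 300 × 0.038 = 11.4 events, and it is tempting to call these missed. They would be complications of the procedure, so they fall inside the window. The range also rests on two values, and the table warns of a single study with higher rates throughout, from which 3.8% appears to come. The thromboembolism range of 0% to 0.32% is for right or left ventricular biopsy; the four large series beside it all show 0%, and only right ventricular biopsy is done here. This stands in full.

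**Not every hold is caused by the research.** Most catheterizations are clinically indicated (4.4), some participants have a clinical biopsy first (3.1), and bridging is left to the patient's clinician. This narrows the affected group but does not empty it: the exclusions are written for biopsy risk, 3.4.b speaks of a hold for the biopsy, and research-only catheterization is allowed.

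**Starting at the intervention is a legitimate choice.** That is fair where exposure begins with the intervention. Here an exposure required by the entry criteria begins earlier.

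**Conclusion.** The point holds for the pre-procedure interval. Read as written, the protocol requires anticoagulation to be stopped or lowered before the biopsy and starts recording adverse events only afterwards, with no other data source in between. After the procedure there is no gap in the window, but 3.1, 3.5.c/3.5.d, the 4.4 table and 5.0 do not agree on what is collected and need to be reconciled.

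The number of missed events cannot be derived from the protocol and is likely small. Only anticoagulated participants are affected, and among them only those whose hold is made for the research biopsy and follows consent. A reader might also infer that participants are not told of the risk of interruption. That cannot be judged, because the consent pages are not available. The case for a change is that it is cheap and closes a blind spot in safety monitoring, not that a large bias has been shown. No position is taken on how anticoagulation should be managed.

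**What to change.** Change data collection only:

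1. In 5.0 (Adverse Events), for consented participants, open the window at the first anticoagulation change made for the research biopsy, including the start of any bridging, and otherwise at the start of the procedure. State that it opens even if the biopsy is then not done.
2. Add stroke/TIA, systemic embolism, deep vein thrombosis/pulmonary embolism and bridging-related bleeding to 3.5.c and 3.5.d, so that they agree with the 4.4 table.
3. Record whether anticoagulation was interrupted for the research biopsy, with hold and restart dates.
4. Align the discharge and 30-day form in 3.1 with 5.0: collect all adverse events and record attribution as a separate field.

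The cost is a sentence or two of protocol text and a few form fields, largely completed from records that are already reviewed. No procedure or visit is added. The downside is that the reported complication rate may look slightly less favourable.
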